8.1.1 Definition of Phase II and exploratory endpoints and Analytic Plan

The phase II dose will be determined by an initial standard '3+3' phase I component as described in Section 4.1. Once a RP2D is reached, the phase II will begin.

Definition of phase II primary endpoint: Progression free survival at 8 and 16 weeks using RECIST v 1.1, defined from date of treatment initiation to date of progression according to RECIST or death, or is censored at the date of the last imaging. If patient is not evaluated at 8 and/or 16 weeks then the patient is not considered as alive and progression-free.

Definition of secondary outcomes/endpoints:

1. Composite of unacceptable toxicity at 8 weeks (grade 4 non-hematologic toxicity thought to be definitely, probably or possibly related to study drug)
2. Overall response using RECIST v1.1.

Definition of exploratory objectives:

1. Changes in STAT1 phosphorylation and MHC1 up regulation in PBMCs from baseline to week 2, 3, 7, EOT.
2. Degree of desmoplasia in archived FFPE tumor samples and change in serum IL-6
3. Degree of nuclear NF- κ B p65 and STAT1 in archived FFPE tumor samples

Analytic plan for primary and secondary objectives:

Kaplan Meier curves will be used to estimate the distribution of progression free survival, median survival, and 1-year survival. Proportions, 95% confidence intervals, will be used to characterize composite rate of unacceptable toxicity and overall response rate. All analyses are for estimation only, and no larger inference will be generated given the sample size of the study.

Analytic plan for exploratory objectives:

Pre- and post- treatment phosphorylation changes in pSTAT1 and MHC1 (flow data, the MFIs will be log10) and serum IL-6 will be analyzed by paired t-tests. Degree of desmoplasia and nuclear NF- κ B and STAT1 will be quantified using standard immunohistochemical methods. Statistical analysis for western blots and responders vs non-responders tumor immunohistochemistry will be performed using non-parametric Mann-Whitney test and/or paired t-tests.

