8.1.2 Sample Size Determination

The design incorporates two conditions not usually treated. First, the final group of patients in the phase I component is considered part of the phase II trial. Second, the phase II part has two end-points, toxicity (UT: unacceptable toxicity) and efficacy. The relation between toxicity and efficacy is explicitly taken into account. We test the composite null hypothesis:

$H_0: p(UT) > 0.25 \text{ or } p(PFS > 8 \text{ weeks}) < 0.5 \text{ or } p(PFS > 16 \text{ weeks}) < 0.35$

versus the alternative:

$H_1: p(UT) < 0.05 \text{ and } p(PFS > 8 \text{ weeks}) > 0.66 \text{ and } p(PFS > 16 \text{ weeks}) > 0.56.$

Eleven new patients will be treated in the first stage of the phase 2 component. If 3/17 patients have UTs OR if at most 8/17 are alive and PF at 8 weeks the trial will be either be

suspended for excess toxicity or for futility. The decision for early termination (or amendment) is based on these cut points. If either 3 of 17 stage I patients are DLTs OR if at most 8 of 17 are PF at 8 weeks then terminate or hold up. The final decision point, PFS at 16 weeks is not relevant; the number of such patients does not influence the early decision. The confusion seems to relate to the alternative hypothesis which is couched in terms of 'AND'. It does, of course, require both early and late components of the outcome to be defined. Finally, although 3/17 is less than 0.25, this is the cut point, clearly between 0.05 and 0.25. The early PFS cut point 8/17 is less than 0.5 but is only a cut point.

At that point we will consider protocol amendment. Otherwise, 17 new patients will be recruited. If at least 14/34 patients are PF at 16 weeks AND less than 4/34 have UTs the null hypothesis will be rejected and the treatment declared efficacious. Otherwise it will be declared either too toxic or not efficacious.

Further operating characteristics and statistical details can be found in Appendix 12.3

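### The analysis planned for the primary endpoint (Kaplan-Meier, for estimation only) is not the count that decides the trial, and that count has no planned estimate or interval

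*Combined protocol and SAP*

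**What the plan says.** Section 8.1.1 defines the phase II primary endpoint as PFS at 8 and 16 weeks. The definition holds two rules for incomplete follow-up. A patient without an event "is censored at the date of the last imaging". The next sentence says: "If patient is not evaluated at 8 and/or 16 weeks then the patient is not considered as alive and progression-free".

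The analytic plan for the primary and secondary objectives, in the same section, says: "Kaplan Meier curves will be used to estimate the distribution of progression free survival, median survival, and 1-year survival". It plans proportions with 95% confidence intervals for unacceptable toxicity (UT) and overall response, but not for PFS at 8 or 16 weeks. It closes: "All analyses are for estimation only, and no larger inference will be generated given the sample size of the study".

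Section 8.1.2 says "We test the composite null hypothesis". The null is UT above 0.25, or 8-week PFS below 0.5, or 16-week PFS below 0.35. The stage 1 rule is a count: "If 3/17 patients have UTs OR if at most 8/17 are alive and PF at 8 weeks", the trial is suspended. At the end, with at least 14/34 progression-free at 16 weeks and fewer than 4/34 UTs, "the null hypothesis will be rejected and the treatment declared efficacious". Any other result is declared too toxic or not efficacious. Appendix 12.3 tabulates type I error and power for this count rule.

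Two other places bear on who is counted. Section 4.3 includes all patients in the PFS analysis. Section 9 requires at least one cycle and a disease re-evaluation before a patient is evaluable for PFS.

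**The concern.** Sections 8.1.1 and 8.1.2 are adjacent and describe different primary analyses. One is a descriptive survival curve with censoring. The other is a hypothesis test on a proportion with a fixed denominator. An analyst who follows 8.1.1 as written produces no estimate and no interval for the quantity that decides the trial.

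The two summaries also treat a missing scan differently. Censoring takes the patient out of the risk set; the landmark rule makes the patient a failure. The plan does not say which rule belongs to which analysis, and section 9 adds a third handling by removing such patients from the evaluable set. In an open-label, single-arm trial this leaves room to choose after the data are seen which 16-week figure to put forward. The curve is the more favourable one.

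**Working it through.** **1. The plan's own figures.** Inputs from 8.1.2 and Appendix 12.3:
- Stage 1 has 17 patients and stops at 3 or more UTs, or at 8 or fewer progression-free at 8 weeks. There is at most 1 UT in the first 6.
- Stage 2 adds 17 patients. Success is at least 14 progression-free at 16 weeks and at most 3 UTs.
- Half of the toxicity falls in the first 8 weeks. *a* is the joint probability of UT and being progression-free at 16 weeks.

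Exact enumeration gives, with UT = 0.05:

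| | a = 0 | a = 0.05 |
|---|---|---|
| Power, 16-week PFS 0.56 | 0.8759 | 0.8099 |
| Type I error, 16-week PFS 0.35 | 0.2116 | 0.1054 |

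These match the appendix to four decimals, provided that first-8-week UTs in the initial cohort are left out of the final UT count. So the stated operating characteristics belong to the count rule. None is given for a Kaplan-Meier estimate.

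**2. Can the curve and the count disagree?** Take 34 patients with scans at nominal weeks 8 and 16: 11 progress by week 8, 2 are last imaged at week 8, 8 progress between weeks 8 and 16, and 13 are progression-free at week 16 (11 + 2 + 8 + 13 = 34).
- Count: 13/34 = 38.2%. The cut is 14/34 = 41.2%, so the rule fails.
- Kaplan-Meier: (1 − 11/34) × (1 − 8/21) = 23/34 × 13/21 = 41.9%.

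A stage 1 example: of 17 patients, 8 are progression-free, 7 have progressed and 2 are never re-imaged.
- Count: 8/17 = 47.1%, which meets the futility rule.
- Kaplan-Meier: 1 − 7/15 = 53.3%. Dropping the two under the section 9 evaluability rule gives the same figure, 8/15 = 53.3%.

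The direction is fixed. With scans at nominal times, Kaplan-Meier shares a censored patient's weight among those still at risk, while the count gives that weight to failure. The curve is therefore at or above the count, and equals it when nobody is unevaluated.

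**3. Expected size.** The documents give no missed-scan rate, so the rates here are assumptions. With true 16-week PFS of 0.56 and a fraction L of progression-free patients unevaluated at week 16, the expected count is 34 × 0.56 × (1 − L):

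| L | Expected count | Proportion |
|---|---|---|
| 0 | 19.0 | 56.0% |
| 5% | 18.1 | 53.2% |
| 10% | 17.1 | 50.4% |
| 15% | 16.2 | 47.6% |

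All are above 14.

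**4. How often might they fall on opposite sides of 14/34?** Assume independent loss of 3%, 5% or 10% in each of the two scan windows, n fixed at 34, no stage 1 stop and no toxicity criterion. In simulation with true 16-week PFS of 0.56, the mean counted proportion is about 53%, 51% and 45%, while mean Kaplan-Meier stays at 56%. The count fails with the curve at or above 14/34 in 2.2%, 5.6% and about 20% of trials. The reverse never occurs.

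**5. What interval would accompany the count?** Exact (Clopper-Pearson) 95% lower limits are 24.6% at 14/34, 32.4% at 17/34 and 35.1% at 18/34. Every result from 14 to 17 passes the rule with an interval that includes the null value of 0.35. This is expected, because the rule's type I error with low toxicity is 10% to 21%.

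**The case against.** The strongest reply is that the trial's conclusion is not in doubt. A reader might infer that it is left undefined between estimating and declaring efficacy. The documents do not support that: 8.1.2 covers every outcome, Appendix 12.3 evaluates that rule, and Kaplan-Meier has no part in the decision.

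A reader might also infer that 8.1.1 forbids the test in 8.1.2. The sentence disclaims a *larger* inference and closes a paragraph on curves, toxicity and response, so it may be meant only for conclusions beyond the go/no-go rule. That reading is possible, but the sentence covers all analyses under a heading that includes the primary objective, so the wording needs repair.

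Third, no 16-week Kaplan-Meier value is planned; the plan names the PFS distribution, median survival and 1-year survival. This stands. A 16-week figure would be read off the curve because the endpoint is PFS at 8 and 16 weeks, not because the plan asks for it.

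Fourth, censoring for a curve and failure-coding for a landmark count can coexist, and the failure rule is already in 8.1.1. This also stands; what is missing is a statement of which rule serves which analysis.

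Finally, a reader might infer that missed scans would usually change the decision. The expected counts in step 3 all clear the cut, and the disagreement in step 4 compares a curve with a cut set for a count.

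**Conclusion.** The concern holds as a mismatch between the stated primary analysis and the decision rule, not as a missing or unworkable decision. Three facts need no assumption: 8.1.1 calls all analyses estimation while 8.1.2 rejects a null hypothesis; no estimate or interval is planned for the deciding proportions; and censoring and failure-coding stand in one definition without being assigned.

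The numerical gap exists only if patients go unevaluated, and its size rests on assumed loss. Two missed scans among 34 can put the curve (41.9%) and the count (38.2%) on opposite sides of 41.2%. On average, with 5% to 15% of progression-free patients missed at week 16 and true PFS of 56%, the count loses about 1 to 3 patients and still passes. It should be corrected; it does not invalidate the design.

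**What to change.** - State that the primary analysis is the proportion alive and progression-free at 8 and 16 weeks in all phase II patients counted in 8.1.2, with unevaluated patients as failures, judged by the 8.1.2 rule.
- Report each proportion with a confidence interval labelled descriptive. Note that the rule's type I error is 10% to 21% when toxicity is low, that a 95% interval will include 0.35 for 14 to 17 of 34, and that a naive exact interval ignores the two-stage stopping. The interval must not become a second test.
- Label Kaplan-Meier, with censoring at last imaging, as supportive.
- Limit the estimation-only sentence to analyses other than the 8.1.2 rule.
- Align the section 9 evaluability rule for PFS with this definition and with section 4.3.

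The cost is wording, one more proportion and interval at each time point, and a reported PFS that may be slightly less favourable than the curve.

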Extensive work has been done examining IFN in those with metastatic RCC.¹⁵⁻¹⁷ IFN-alpha is approved by the FDA to be used in combination with bevacizumab based on two phase III trials that demonstrated a progression-free survival (PFS), but not an overall survival (OS) benefit.^{18,19} In first line setting, an overall response rate (defined as complete response (CR) + PR) of ~7%-15% can be expected with single agent IFN with a 30%-50% SD rate. Furthermore, combinations of IFN with other drugs such as sorafenib,^{20,21} sunitinib,²² IL-2,²³ fluorouracil,¹⁷ and monoclonal antibody therapy²⁴ has been attempted with a manageable side-effect profiles and at times efficacy signals. Furthermore, pegylated IFN has been studied in RCC with comparable results and toxicity profile to standard IFN, but allowing for once weekly administration.²⁵⁻³⁰ Given the rapid rise in VEGF and mTOR directed therapy for mRCC over the last 5-8 years, IFN is infrequently used as a first line therapy today. Nevertheless, none of the recently approved agents for mRCC are curative and the most common response remains stabilization of disease. Thus, further development of a novel IFN based combination based on sound scientific rationale makes sense as it may provide an additional option in the armamentarium for mRCC patients who have failed first line therapy.

Previous clinical experience with proteasome inhibition (bortezomib) in RCC

Two clinical trials of bortezomib in patients with RCC have been reported. After establishing a dose level in a phase I trial³¹, Kondagunata et al treated 37 patients at a dose of 1.3-1.5 mg/m² twice weekly, on a two week on, one week off schedule.³² Eighteen patients were treatment naïve and sixteen received IFN previously. Bortezomib was given i.v. twice weekly. Partial response (PR) rate was 11% with 3 patients experiencing long-term PRs (8-20 + months); stable disease (SD) rate was 38%. Common Grade 2 or higher adverse events (AEs) included constipation, fatigue, neuropathy and dyspnea. A similar study by Davis et al treated 21 patients with only a single objective PR, thus leading to study termination.³³ Though efficacy overall was modest in this study, bortezomab did show antitumor activity as a single agent for some RCC patients. Given the similarity between bortezomib and Ixazomib, we would expect similar findings with Ixazomib.

Previous clinical experience combining IFN with bortezomib

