Based on preclinical work by Lesinski et al³⁴, a phase I trial of fixed dosed IFN-alpha 2b (5 MU/m² s.c three times a week) with escalating doses of bortezomib once a week (1.0 mg/m², 1.3 mg/m² and 1.6 mg/m² dose levels) in metastatic melanoma patients was conducted, reported at the ASCO 2013 annual meeting and the manuscript is currently

submitted for review.³⁵ A total of 16 patients were enrolled with most common Grade 3 toxicity being fatigue, vomiting and diarrhea. Grade 4 toxicity observed was fatigue and lymphopenia. 1 PR, 7 SD and 8 progressive disease (PD) were observed with a median PFS and OS of 2.5 and 10.3 months respectively. Based on this phase I study, a weekly dose of 1.3 mg/m² of bortezomib was found to be safe in combination with IFN-alpha 2b. Correlative work showed a decrease in pro-angiogenic factors in the patient with a PR. This work supports the notion that combining IFN with a proteasome inhibitor is feasible and we propose to extend it to ixazomib.

Study Rationale: Based on strong preclinical data showing complementary and novel anti-tumor activity of IFN and bortezomib in RCC noted in the [name] laboratory, we propose a phase I/II trial of combination pegylated IFN-alpha 2b with ixazomib in metastatic RCC patients who have failed at least two prior lines of therapy. We hypothesize that by disabling NF- κ B via ixazomib, we can promote IFN induced necrotic cell death of RCC. We hypothesize that the combination of ixazomib with IFN will lead to increased necrotic cell death in RCC tumors and consequent clinical benefit to patients.

Ixazomib

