2. STUDY OBJECTIVES

Phase I Primary Objective

1. To determine the safety, tolerability and RP2D of the combination of pegylated interferon with ixazomib.

Phase II Primary Objective

1. To determine progression free survival (PFS)

Phase II Secondary Objectives

1. To determine the composite rate of unacceptable toxicity at 8 weeks
2. To determine the overall response rate (ORR) using RECIST v1.1

Phase II Exploratory Objectives

1. To examine changes in STAT1 phosphorylation and MHC1 up regulation in PBMCs as an indicator of IFN activity
2. To use archived FFPE tumor tissue to correlate activated tissue stroma (i.e., desmoplasia) with serum IL-6 levels and patient outcomes
3. To use archived FFPE from past biopsies for IHC analysis of nuclear NF-κB p65 and phospho-STAT1 in order to test whether those patients with the most apparent constitutive pathway activation related to either of these two markers are generally more or less responsive to the combination therapy.

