4. STUDY DESIGN

The study will be conducted at a single center: Fox Chase Cancer Center. It will be open label and non-randomized. It will begin with a '3+3' phase I component to assess initial safety, tolerability and RP2D, followed by a phase II using a two-stage design previously described.⁴⁹ The design is meant to incorporate an early stopping rule for futility and toxicity, and to allow for an endpoint of PFS at 8 and 16 weeks rather than overall response. We believe PFS is a more valid endpoint given the scientific rationale of tumor necrosis rather than apoptosis resulting in radiographic disease stabilization rather than shrinkage. The overall treatment plan can be seen in Schedule of Events (page 6) and Figure 4-1.

Figure 4-1: Study Schema

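### The tissue markers are planned to be compared only between undefined responders and non-responders, and no method relates them to PFS, the outcome on which the protocol expects the benefit to show

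*Combined protocol and SAP*

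**What the plan says.** The analytic plan for exploratory objectives (section 8.1.1) covers two assays in one sentence: "Statistical analysis for western blots and responders vs non-responders tumor immunohistochemistry will be performed using non-parametric Mann-Whitney test and/or paired t-tests". It defines neither responder nor the pairing of tests with assays.

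Other sections bear on this:

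- Section 4 prefers PFS to overall response because the mechanism is "tumor necrosis rather than apoptosis resulting in radiographic disease stabilization rather than shrinkage".
- Section 2 asks for desmoplasia to be correlated "with serum IL-6 levels and patient outcomes", and asks whether constitutive p65 or phospho-STAT1 activation marks patients who do better or worse on the combination.
- Section 4.6 says that palladin staining will be correlated with clinical parameters and outcomes, and names no method. Palladin is scored in four ordered levels.
- Response as a rate is complete plus partial response (section 1); section 9 gives the RECIST 1.1 criteria.
- Archival tissue is optional (Schedule of Events, footnote 15).

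**The concern.** The tissue objectives ask whether pathway activation or desmoplasia marks the patients who benefit. The protocol expects benefit to appear as disease control, but the only comparison it names sorts patients by response. If response means RECIST CR or PR, a patient stable for a year falls in the same group as one who progresses at week 8.

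Two consequences follow. The responder group is likely to be very small. And if a marker tracks disease control, the non-responder group mixes patients who benefit with patients who do not, which pulls the observed difference toward zero. The trial would collect tissue and PFS on the same patients without a stated method to connect them.

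**Working it through.** The documents give no sample size, effect size or power for the marker comparisons, so there is no figure of the plan's own to reproduce.

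**Inputs**

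- Response rates cited in section 1: for first-line interferon, "an overall response rate (defined as complete response (CR) + PR) of ~7%-15% can be expected with single agent IFN"; for bortezomib in RCC, "Partial response (PR) rate was 11% with 3 patients experiencing long-term PRs" (37 patients) and "treated 21 patients with only a single objective PR" (1/21 = 4.8%); for interferon plus bortezomib in melanoma, "1 PR, 7 SD and 8 progressive disease (PD) were observed" (1/16 = 6%). Range used: 5% to 15%. None of these is a projection for this combination after at least two prior lines; the range is an assumption.
- Patients: 34 in the phase II decision rule (section 8.1.2). The exploratory endpoints cover both phases (section 3), so the upper bound is 18 + 31 = 49 (section 4.3).
- Progression-free at 16 weeks: 0.35 (null) and 0.56 (alternative), section 8.1.2.

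**Group sizes**

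- Responders of 34: 34 × 0.05 = 1.7 to 34 × 0.15 = 5.1, so about 2 to 5.
- Responders of 49: 49 × 0.05 = 2.5 to 49 × 0.15 = 7.4, so about 2 to 7.
- Progression-free at 16 weeks, of 34: 34 × 0.35 = 11.9 and 34 × 0.56 = 19.0, so 12 v 22 to 19 v 15.

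**Chance of too few responders (binomial, n = 34)**

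| Response rate | No responder | At most one |
|---|---|---|
| 5% | 17% | 49% |
| 7% | 8% | 30% |
| 11% | 2% | 10% |
| 15% | 0.4% | 3% |

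With one responder of 34 the smallest two-sided exact Mann-Whitney p is 2/34 = 0.059, so the 5% level cannot be reached.

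**Power** (exact two-sided Mann-Whitney at 5%, normal marker, assumed 1 SD difference, 3,000 simulated trials). The last column is (1.96 + 0.84) × √(1/m + 1/n), the difference detectable at 80% power.

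| Split of 34 | Power | Detectable at 80% |
|---|---|---|
| 2 v 32 | 21% | 2.0 SD |
| 3 v 31 | 32% | 1.7 SD |
| 4 v 30 | 41% | 1.5 SD |
| 5 v 29 | 47% | 1.4 SD |
| 12 v 22 | 74% | 1.0 SD |
| 19 v 15 | 78% | 1.0 SD |

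A repeat with 20,000 trials agreed within two percentage points in every row.

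**If the marker tracks progression-free status instead.** Suppose the 1 SD difference lies between patients who are and are not progression-free at 16 weeks, and all responders are progression-free. With 19 progression-free and 5 responders, 14 of the 29 non-responders are progression-free, and the expected difference shrinks to 1 − 14/29 = 0.52 SD. With 2 responders it is 1 − 17/32 = 0.47 SD. With 12 progression-free it is 1 − 7/29 = 0.76 SD (5 responders) or 1 − 10/32 = 0.69 SD (2 responders). Simulated power of the responder split is then about 6-14% (19 progression-free) or 9-27% (12 progression-free).

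All of these figures assume tissue from all 34 patients. Ties in the palladin score and missing tissue would lower the power of both splits.

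**The case against.** Several points on the other side have force.

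- **Responder may be meant more broadly.** Section 1 calls stabilization the most common response to recent agents. If stable disease counted, the small-group problem would go. But 8.1.1 does not say so, and the only formal definition is CR/PR. The gap in definition stands.
- **Section 4.6 already promises an outcome correlation for palladin.** True, and the plan therefore does not intend to ignore outcomes. It names no method there, and 8.1.1 supplies none for any tissue marker.
- **The power comparison depends on its assumptions.** It gives both splits the same 1 SD difference. At 1.5 SD, 5 v 29 has about 82% power; at 0.75 SD, 12 v 22 has about 49%. Pooling both phases also helps: about 34% for 3 v 46 and 62% for 7 v 42. The figures are illustrative only.
- **PFS has its own weakness.** In a single arm it mixes prognosis with treatment effect, and section 4.6 expects high desmoplasia to mean both worse outcome and better response, which could offset each other. Patients not evaluated at 16 weeks also count as not progression-free. This stands as a limit on interpretation.

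A reader might also infer that the named tests are wrong or cannot be run. The documents do not support that. The western blots use serial PBMC samples, where a paired test is valid, and Mann-Whitney suits archival tissue from independent groups. Mann-Whitney fails outright only with no responders. A paired test could not compare two independent groups, but the sentence need not be read as proposing that, and the specimen sheet allows on-treatment tissue from some consenting patients. The defect is an unstated assignment.

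**Conclusion.** The point holds as a minor one. The one tissue comparison named in 8.1.1 uses an undefined responder split which, on the only formal definition, is the outcome the protocol set aside in favour of PFS, and no stated method relates any marker to PFS. On the assumed 5-15% response rate, about 2-5 of 34 patients (2-7 of 49) would be responders. For a 1 SD normal marker, power is about 21-47%, against 74-78% for the 16-week progression-free split.

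The advantage of the PFS-based split rests on the benefit showing as disease control, as section 4 expects. It also rests on a response rate borrowed from other settings. A reader might infer a threat to the trial's main result; there is none. No stopping rule, sample size or efficacy decision in 8.1.2 uses these markers.

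**What to change.** Replace the sentence in 8.1.1 with text along these lines:

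> Palladin, nuclear p65 and STAT1 scores and baseline IL-6 will each be related to PFS by Cox regression, with the marker as a continuous or ordinal term, and compared between patients who are and are not progression-free at 16 weeks by the Mann-Whitney test. Pre- and post-treatment PBMC western blot values will be compared by a paired test. RECIST response (CR or PR) will be listed descriptively with the marker values.

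Add that these are exploratory associations which, without a control arm, cannot separate prognosis from treatment effect. Report how many patients are classed as not progression-free only because the 16-week evaluation is missing. The Cox analysis does not share that classification, because 8.1.1 censors PFS at the last imaging. State also whether phase I patients are included.

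The cost is one paragraph. PFS and the marker data are already to be collected, so no new patients, samples or visits are needed.
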